### 4.2.2 Blinding

The trial will be open-label i.e., participant, investigator and sponsor will be unblinded to treatment and meal conditions assignation. Therefore, after treatment allocation by the site pharmacist according to the randomisation schedule, the study investigators will be provided with the explicit details related to the treatment (Part 1) or feeding conditions (Part 2).

## 4.3 Study duration and duration of participant's participation

Post administration duration of the study will be 30 days, plus the screening period of 7 to 45 days.

It is estimated that the clinical portion of the study will be completed in approximately 4-6 months.

## 4.4 Schedule of events

## Abbreviations:

D: Day (where Day 1 is the first day that IMPs are administered)

### TBS: Thick Blood Smear

## FSH: Follicular Stimulating Hormone

### LABELS at Screening Period:

\* Procedures must be completed within specified window ( $\pm$ ), with ECG and vitals performed prior to blood sampling

\*\* Contraception must be started for at least 30 days prior to dosing

x Written informed consent must be obtained prior to any study procedures.

$x^A$  procedures must be repeated if performed >45 days prior to D1. Repeating the procedure will result in a 15-day delay to D1.

**xB** procedures must be repeated if performed >15 days prior to D1. **VS** questionnaires to be completed within 12 minutes of IMP during

Xc questionnaire to be completed within 10 minutes of IMP dosing  
[#] Blood volume in ml

[#] Blood volume in mL

Note: COVID-19 tests will be carried out at regular intervals, prior to entry in the unit and throughout the residential period as per the latest COVID-19 Infection Control Guidelines and pre-entry algorithms

#### **4.5 Safety hold and early termination of the study**

If either of the following pausing criteria are met, trial activities will be put on temporary hold and the SRC chair will be consulted in order to perform thorough evaluation:

- Severe non-serious adverse reactions considered as, at least, possibly related to the IMP administration in two subjects in the same part, independent of within or not within the same system-organ-class.
- One participant experiences an SAE deemed related to study product administration.

If either of these two criteria is met by participants who received either of the study PQP products, the principal investigator (PI) will inform the sponsor for initiation of a temporary hold. After confirmation of the temporary hold, the Sponsor will request an ad hoc meeting of the SRC to review the event(s) and any associated safety data. Following the SRC review and recommendation, a decision will be made by the PI and the Sponsor to either trigger a longer-term safety hold, terminate the study, or resume administration of investigational product. The Institutional Review Boards (IRBs), ethical committee and regulatory authority will be promptly informed of this event, recommendations and decisions.

Irrespective of the temporary hold criteria, the Sponsor, PI or applicable ethical committees or regulatory agencies may decide to put the study on hold based on any other constellation of AEs, or based on any other legitimate reason, such as:

- Ethical concerns
- Safety issues with the study drug
- When the safety of the participants is doubtful or at risk
- Inaccurate or incomplete data
- Administrative decision
- Unforeseen events such as endemic/pandemic

If a safety-hold or study termination is deemed necessary, the applicable ethical committees and regulatory agencies will be notified. For a safety hold to be lifted, there must be a written concurrence by the entity or entities that initiated the hold that the study can resume.

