## 8.2 Grading of adverse events

### 8.2.1 Standard Toxicity Grading

For each AE, the Investigator will assess the maximum severity. In general, All AEs/SAEs (except laboratory abnormalities) will be graded by the Investigator using the AE severity grading according to the WHO system:

WHO intensity grades are defined as follows:	
1	Mild – No interference with routine activity.
2	Moderate – Interferes with performance of some activities of daily living, but responds to symptomatic therapy or rest.
3	Severe – Significantly limits ability to perform activities of daily living despite symptomatic therapy.
4	Very severe – Incapacitates patient despite symptomatic therapy; requires hospitalization

WHO Handbook for Reporting Results of Cancer Treatment. WHO Offset Publication No. 48. World Health Organization; Geneva, Switzerland. 1979:16–21.

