## 8.2.2 Grading of abnormal values for safety laboratory assessments

The site manual for the reference intervals and grading for selected abnormal values, utilizes the population references for specified laboratory parameters to grade abnormal laboratory values using adopted schemes of reference for toxicity grading (17, 18, 19).

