## 8.2.3 Abnormal assessments to be considered as adverse events

Each abnormal value will additionally be classified as clinically significant or not clinically significant according to the clinician's medical judgment. In general, abnormalities that require intervention will be classified as clinically significant. Borderline abnormal laboratory findings and other objective measurements should NOT be routinely captured and reported as AEs, as they will be collected and analysed separately. However, abnormal laboratory findings or other objective measurements that meet the criteria for an SAE, result in discontinuation of the IMP, require medical intervention or are judged by the Investigator to be clinically significant changes from baseline values should be captured and reported on the AE pages of the eCRF.

When recording an abnormal laboratory finding on the AE pages of the eCRF, a clinical diagnosis should be provided rather than the abnormal value itself, if this is available (for example, "anaemia" rather than "decreased red blood cell count" or "haemoglobin = 10.5 g/dL").

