## 8.4 Serious adverse events

An AE/AR is defined as serious if:

- it results in death;
- it is life-threatening (the term "life-threatening" in the definition of "serious" refers to an event in which the subject was at immediate risk of death at the time of the event; it does not refer to an event which hypothetically might have caused death if it was more severe);
- it requires a hospitalisation or prolongs existing hospitalisation;
- it results in persistent or significant disability/incapacity;
- it is a congenital abnormality/birth defect;
- it is considered medically important (medical and scientific judgement should be exercised in deciding whether other AE/ADRs are to be considered serious, such as important medical events that may not be immediately life-threatening but may jeopardise the subject or may require intervention to prevent one of the other outcomes listed in the definition above. Examples of such events are intensive treatment in an emergency room or at home for allergic bronchospasm; blood dyscrasias; convulsions that do not result in hospitalisation; development of drug dependency or drug abuse).
- For the purpose of this protocol an AE will be considered as serious should the AE constitute a possible Hy's Law case (defined as a subject with any value of ALT or AST greater than or equal to 3x ULN together with an increase in bilirubin to a value greater than 2xULN (>35% direct) and NOT associated to an ALP value greater than 2xULN).

A non-serious AE/ADR is any symptom or sign which does not fulfil any of the above-mentioned seriousness criteria.

The causality of SAEs (i.e. their relationship to study treatment) will be assessed in the same way as for non-serious AEs.

Note that SAEs that could be associated with any study procedure should also be reported.

A SUSAR is any SAE where a causal relationship with the IMP is at least a reasonable possibility, but is not listed in the Investigator Brochure and/or Summary of Product Characteristics (SmPC).

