## 8.7 Recording of adverse events

All (serious and non-serious) AEs detected by the Investigator or delegates, or spontaneously notified by the subject at each visit/examination must be reported in the respective section of the CRF.

The following information should be reported for each AE, whether or not it can be attributed to the trial drug:

- description of AE
- date of onset/date of resolution
- characteristics of the event (seriousness, intensity)
- actions taken (treatment required must be reported in the eCRF)
- outcome
- relationship with trial drug (causality assessment) and/or study participation

Findings and values related to physical examinations and measurements of ECG, vital signs, (axillary temperature, blood pressure, and heart rate) and laboratory parameters will be defined as AEs if they are considered clinically relevant deteriorations compared with baseline and pre-dose values, as judged by the Investigator.

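### The Section 4.5 pausing criteria contain no QTcF value, and asymptomatic QTcF prolongation would generally be Grade 1 and not count toward criterion 1

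*Protocol*

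**What the plan says.** Protocol 4.5 has two pausing criteria. The first is "Severe non-serious adverse reactions considered as, at least, possibly related to the IMP administration in two subjects in the same part". The second is a single SAE judged related to study product. Outside these, the sponsor, the PI, ethics committees or regulators "may decide to put the study on hold based on any other constellation of AEs, or based on any other legitimate reason", and the listed reasons include drug safety issues and doubt about participants' safety.

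On severity, 8.2.1 states: "In general, All AEs/SAEs (except laboratory abnormalities) will be graded by the Investigator using the AE severity grading according to the WHO system". Grade 1 on that scale is "No interference with routine activity". Grade 3, the grade named severe, needs marked limitation of daily activities despite treatment of symptoms. Grading by numeric value appears only in 8.2.2, where the site manual "utilizes the population references for specified laboratory parameters to grade abnormal laboratory values".

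An ECG finding can become an adverse event in two places. Section 8.2.3 says that abnormal findings which, among other routes, "are judged by the Investigator to be clinically significant changes from baseline values should be captured and reported on the AE pages" of the eCRF. Section 8.7 treats "Findings and values related to physical examinations and measurements of ECG, vital signs" and laboratory results as adverse events when the investigator considers them a clinically relevant worsening. Neither section gives a threshold.

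Section 8.4 makes an event serious if "it is considered medically important (medical and scientific judgement should be exercised in deciding whether other AE/ADRs are to be considered serious". The same section makes a possible Hy's Law case serious on numeric liver limits alone.

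QTcF limits appear as an entry criterion (5.2.2, above 450 ms excluded) and as summary categories in Protocol 10.6 and SAP 17.2 (above 450, 480 and 500 ms; rises above 30 and 60 ms). Neither 10.6 nor SAP 17.2 is linked to 4.5.

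**The concern.** QTc prolongation is the measurable, concentration-related risk that the protocol itself names (2.1.5). The same section makes the view that piperaquine is not torsadogenic conditional on fasted dosing and control of other risk factors. It also cites regulatory advice against giving the DHA combination with food, because of QTc. Part 2 doses all 36 participants after a meal or milk.

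The Part 2 dose is chosen so that predicted fed exposure stays at or below that of 960 mg fasted tablets (2.2), but that is a prediction for a new formulation. The decision to start Part 2 rests on fasted Part 1 data. If the prediction failed, the ECG is where it would be expected to show. The written two-subject rule, applied as it stands, would generally not respond unless the events had symptoms. Dosing of the remaining participants could then continue until someone chose to intervene.

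**Working it through.** **Step 1: trace an asymptomatic QTcF rise through the rules.**

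| Step | Section | Result |
|---|---|---|
| Is it an adverse event? | 8.2.3, 8.7 | If the investigator judges it clinically significant or relevant |
| Which scale applies? | 8.2.1 | The functional WHO scale; ECG is a clinical assessment (7.1.4), not a laboratory test (7.2) |
| Does value-based grading apply? | 8.2.2 | No, laboratory values only |
| Grade without symptoms? | 8.2.1 | Generally 1 |
| Counts toward criterion 1? | 4.5 | Generally no, in any number of participants |
| Counts toward criterion 2? | 4.5, 8.4 | Only if classed as serious and related |

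**Step 2: how often would a numeric limit cause a hold?** The plan gives no figure to reproduce, so this is an illustration.

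Inputs from the documents:
- 36 participants in Part 2, of whom 12 receive the high-fat meal.
- Cut-offs of 500 ms and 60 ms (10.6), and the two-subject rule (4.5).
- Mean prolongation of 15–20 ms in fasted studies, with no dose stated (2.1.5).

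Assumptions:
- One normally distributed QTcF change per participant, SD 12 ms.
- Baselines of 440 ms or lower. Exceeding 500 ms then needs a rise above 60 ms or more, so the 60 ms limit governs.
- High-fat means of 30 and 45 ms. The value 45 is 3 × 15, as if QTc scaled with a 3-fold rise in exposure.

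Formulas: p = 1 − Φ((60 − mean)/SD), and P(hold) = 1 − P(0 events) − P(1 event).

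*All 36 at mean 20 ms.* z = (60 − 20)/12 = 3.33 and p = 0.000429. P(0) = (1 − p)^36 = 0.98467 and P(1) = 36p(1 − p)^35 = 0.01522. P(hold) = 0.000115, about 0.01%.

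*High-fat group only is higher, the other 24 at 20 ms.* With p_h for the 12 and p_o = 0.000429 for the 24:
- P(0) = (1 − p_h)^12 (1 − p_o)^24
- P(1) = P(0) × [12p_h/(1 − p_h) + 24p_o/(1 − p_o)]

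| High-fat mean | z | p_h | P(0) | P(1) | P(hold) |
|---|---|---|---|---|---|
| 30 ms | 2.50 | 0.00621 | 0.9185 | 0.0783 | 0.0032 |
| 45 ms | 1.25 | 0.1056 | 0.2592 | 0.3701 | 0.371 |

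*Only events among the first 24 dosed (8 high-fat, 16 other), high-fat mean 45 ms.* P(0) = 0.4065, P(1) = 0.3870, P(hold) = 0.207, about 21%.

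**Step 3: sensitivity, all 36 at mean 20 ms.** With SD 15, p = 0.00383 and P(hold) = 0.85%. With SD 12 and every baseline at the 450 ms entry limit, a rise above 50 ms suffices, p = 0.00621 and P(hold) = 2.1%. With both, p = 0.02275 and P(hold) = 20%. Using the highest of repeated ECGs would raise these figures; requiring confirmation would lower them.

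**The case against.** The strongest reply is that the trial is already protected. Criterion 2 needs only one related SAE, and a QTcF above 500 ms in a healthy volunteer could readily be called medically important. Section 4.5 lists doubt about participants' safety as a ground for a hold. ECGs are read in real time (5.1), a cardiologist can be consulted (7.1.4), participants stay supervised for 48 hours (2.1.5), and the SRC must clear the move to Part 2. Section 2.1.5 also reports a meta-analysis that found no raised arrhythmia risk with the registered three-day regimen. The planned single 320 mg dose is one-ninth of that regimen's total (320/(3 × 960)).

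All of this stands, and it limits the point. A reader might infer that a QTcF event can never pause the trial. The documents do not support that, because the one-subject SAE route and the discretionary hold are both open. Nor would the data be lost: the SAP tabulates the QTcF categories (Table 14.3.5.6). What remains is that every one of these routes to a hold depends on judgement without a threshold, although 8.4 shows that the protocol is willing to use a numeric, symptom-free trigger for liver findings.

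A reader might also take a large fed effect in all 36 participants as the expected case; at a mean of 45 ms the same model gives 91%. That is extreme. Only 12 participants get the high-fat meal, Section 2 reports no significant effect of local low-fat meals on exposure from the tablet, and the 2.2 dose cap is meant to prevent the 3-fold scaling. Baselines all at 450 ms are likewise an extreme case.

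Finally, calling QTcF prolongation a severe non-serious reaction could steer events away from the stricter SAE route. That objection is sound, and the wording of the fix has to deal with it.

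**Conclusion.** The gap in the written rule is real. Criterion 1 as worded would generally ignore asymptomatic QTcF prolongation of any size, and any hold would rest on judgement. It is worth correcting before Part 2 dosing, but it does not show that participants are unmonitored or that dosing could not be paused.

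The conclusion about criterion 1 follows from the text alone. It depends on 8.2.1 being the scale meant by severe in 4.5; no other scale in the protocol defines that word for non-laboratory events. If the ECG Manual, SRC charter or site grading manual sets QTcF limits, the gap shrinks to a missing cross-reference.

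The hold probabilities (about 0.01% at a uniform 20 ms; 0.3% to 37% for a high-fat mean of 30 to 45 ms; about 21% at the upper end if only the first 24 dosed count) rest on assumed SDs, baselines and fed means. They are neither forecasts nor upper limits. They show that a two-subject limit would respond mainly to a large food effect. Dosing is single-dose, so a hold protects only those not yet dosed.

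**What to change.** Leave the 8.2.1 scale unchanged and add to 4.5:

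> For criterion 1, a QTcF >500 ms or an increase from baseline >60 ms, confirmed by repeat or triplicate ECG and at least possibly related to the IMP, counts as a severe reaction regardless of symptoms or WHO grade. This does not replace assessment of each such event as a possible medically important SAE under 8.4; one such related SAE is enough to trigger criterion 2.

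If another study document already sets QTcF limits, cite them in 4.5 instead.

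The cost is a protocol amendment with sponsor and PI signature and ethics approval (12.9), and some chance of a temporary hold for an asymptomatic finding. That chance is small under the main assumptions at 20 ms, but larger if variability is high or baselines lie near 450 ms. No new procedure is needed, and the WHO grades and SAP severity tables do not change. The sentence still leaves relatedness to judgement, and a single participant above the limit still depends on the SAE assessment.

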## 5 SELECTION OF THE STUDY PARTICIPANTS

### 5.1 Study setting

The study will be conducted at the Bagamoyo Clinical Trial Facility (BCTF) in Bagamoyo, Tanzania where screening, enrolment and follow up of healthy participants will be done. BCTF is part of the Bagamoyo Research and Training Center (BRTC) located on the outskirts of Bagamoyo and therefore has access to the institutional research clinical laboratory with adequate facilities for the conduct of safety and several other assessments. Furthermore, during the study, the site will be equipped with an adequate number of 12-lead ECG machines to record digitalized cardiac parameters, which will be performed and reviewed in real-time by the delegated, experienced study clinician and subsequently transmitted for further assessment centrally by an ECG vendor. The team has several years of experience in the conduct of clinical trials from phase I to IV. The Investigators team have been trained on Protecting Human Research Participants. In addition, the site team has been trained on the principles of ICH-GCP. Regular advanced life support trainings (including certificates) are conducted on site by the emergency unit from Muhimbili National Hospital. The site has a well-equipped emergency care unit for handling medical emergencies and stabilization of participants with the on-call emergency response clinical team whenever there are participants in the facility. The team is trained and certified by the emergency department experts from the Muhimbili National Hospital. There is a standby ambulance for transporting participants, once stabilized, for further intensive care and management under the escort of the emergency response team on-call. The nearest emergency support service department is available within 5 minutes, with intensive care service department available within 30 minutes. The site is supported by the institutional quality assurance team. In addition, the Ifakara Health Institute (IHI) has put a COVID-19 response plan in place containing corresponding precaution measurements that are also implemented at the site.

### 5.2 Recruitment

This study is planned to be conducted in healthy adult participants (male and female, including WOCBP). The expected population is to be enrolled from the study centre catchment area among the residents of Bagamoyo town and surrounding areas of Bagamoyo district. Initial work in the community will only commence after all approvals have been received from the relevant ethics committees and regulatory authority. Local authorities will be informed about the study in order to approach the community. Locally applicable methods of advertisement will be used to disseminate the study advertisement, including flyers and announcements via speakers. Targeted and potential community members will be invited to attend community sensitization meetings which will be conducted at designated community areas and may also involve ward leaders, community health workers as well as key opinion leaders in the community. To ensure adequate delivery of the information, meetings will primarily be conducted in Swahili.

At the community sensitization meetings, Investigators will explain the current burden of malaria in particular among infants and children living in malaria endemic areas. The need for age-relevant formulation for malaria treatment and possible prophylaxis will be discussed in a culturally appropriate manner. Investigators will also explain the concept of the clinical trial and the community members will be made aware of the potential risks and unproven benefits of the investigational product to be used in this trial. The outline of the proposed trial including the rationale, aims and study procedures such as consenting, screening, the need for the use of contraception, randomization, inhouse observation and follow-up process will be shared. It will also be made clear that the study will require screening for malaria and other chronic conditions such as HIV and hepatitis. It will be made clear that screening processes will include a range of criteria to be checked covering clinical status as well as ability to comply with protocol, ethical and regulatory requirements. Moreover, it will be explained that exclusion

from participating in the trial does not mean the potential participant is unhealthy and that, the confidentiality of all this information will be protected. Opportunity will be provided for the community members to ask questions and get responses from the Investigators. Potentially interested participants will be asked to provide details that will enable the study team to generate list of potential participants who will be invited to the clinic-based sensitization meeting at BCTF. During the clinic sensitization meetings, Investigators will provide further details in the participant information sheet on the mechanism of the study product, risks, benefits and procedures such as blood sampling, in-patient stay, follow up visits and the need of efficient contraception. Study team members will discuss the existing understanding of the participants with regards to the study and will share more detailed information and clarify any questions in Swahili. At the same occasion they will confirm that the participants are able to read and write (to ensure adequate informed consent for participants). Those interested and considered as potential participants for screening will be provided with the participant information sheet to read at home and for opportunity to discuss with their family members. Potential candidates will be contacted and invited to a screening visit at the BCTF where they will undergo the individual informed consent process prior to any study screening procedures.

To ensure that enrolment goals are met, this recruitment plan allows for longitudinal screening of participants. In addition, longitudinal compliance with study visits and procedures will be encouraged through the provision of a study calendar to participants, using multiple contact methods (phone calls, home visits by community mobilizers, having names and phone numbers of close contacts), transportation to the BCTF if needed.

Adults will be recruited using a rolling recruitment, screening and enrolment process. This process will continue until all 60 study participants have been enrolled and dosed. The recruitment strategies are based on the experience from previous trials conducted by the clinical team in BCTF aiming to achieve adequate participant enrolment to reach target sample size.

The planned total number of participants for this trial will be 60. This is a pilot BA/FE study and is not formally powered, however 12 healthy adult participants are considered sufficient to characterise the PK of the child-friendly taste-masked granule formulation of PQP.

